#### Where

- mm is the observed value in millimetres for which approximate transformation in millilitres needs to be derived
- mL is the approximate transformation of mm in millilitres
- mm0 is the lower value in millimetres from table 7 compared to mm
- mm1 is the upper value in millimetres from table 7 compared to mm
- mL0 is the known value in millilitres (from table 7) for mm0
- mL1 is the known value in millilitres (from table 7) for mm1

Compliance (%) will be derived based on the sachets/tablets/bottles returned, reported as lost and dispensed and total prescribed dose during the stage considered.

All exposure data will be listed including the overall maximum dose prescribed (unit/day), overall maximum dose prescribed (unit/kg/day) and overall maximum dose received (unit/kg/day). In case subjects received both PA21 and Phoslyra during the study, one listing will be generated to display the list of subjects in that situation.

## 4.7. Efficacy Evaluation

Efficacy analysis will be conducted using the FAS and PPS Populations as outlined below.

All results related to serum phosphorus will be expressed in both mmol/L and mg/dL units.

Standard units (mmol/L) from the laboratory file sent by the external vendor will be used to derive the unit in mg/dL using the following conversion factor: ×3.096, starting from the standardized result.

## 4.7.1. Primary Efficacy Endpoint

The primary efficacy endpoint is the change in serum phosphorus levels from baseline to the end of Stage 1 (i.e. considering the last available value in stage 1) in PA21 group. It is based on central laboratory data; in case of missing data regarding central laboratory data, local laboratory measurements are used (please refer to Section 4.2.8.1 for the imputation to be applied).

The change from baseline in the PA21 group will be analysed using a linear mixed model with treatment, baseline serum phosphorus, age (in categories) at randomisation, region and gender as fixed effects. Summary statistics with the estimate of the adjusted mean change from baseline and its 95%CI as well as the corresponding p-value from the t-test will also be provided.

The SAS code used for the linear mixed model will be as below:

```
proc mixed data=input method=type3;
    class treatment age region gender;
    model chg_end_stage1=treatment age region gender baseline / ddfm=KENWARDROGER solution;
    lsmeans treatment / CL alpha=0.05;
    where treatment='PA21';
    ods output lsmeans=lsm1;
```

run;

The primary efficacy analysis will be repeated on the FAS by the following subgroups:

- Formulation (tablets only/sachets only/both)
- Serum phosphorus at baseline according to the age related normal range (above, within + below; see Table 5)
- Age group at randomisation (0-<2, 2-<6, 6-<12, 12-<=18) \* Serum phosphorus at baseline according to the age related normal range (above, within + below; see Table 5). In case of no subject in an age group, this category will not be displayed.

Sensitivity analyses will include a repeat of the primary analysis on the FAS population based on observed data from the central laboratory only (with no imputation by local laboratory data).

Homogeneity of the results of the primary endpoint will be investigated on the FAS population by displaying summary statistics of change from baseline with the estimate of the adjusted mean change from baseline and its 95%CI for the following subgroups using the same linear mixed model as above:

- By age group at randomisation
- By gender
- By region

## 4.7.2. Secondary Efficacy Endpoints

For the following secondary endpoints, summary statistics with 95%CIs for the mean change will be provided by treatment group using the same linear mixed model as for the primary efficacy endpoint:

- Change in serum phosphorus levels from baseline to the end of Stage 1 in Phoslyra group
- Change in serum phosphorus levels from baseline to the end of Stage 2 in both groups

The above secondary endpoints are based on central laboratory data; in case of missing data regarding central laboratory data, local laboratory measurements are used (please refer to Sections 4.2.8.1 and 4.2.8.2 for the imputation to be applied).

Serum phosphorus values over time will be summarised by treatment group using descriptive statistics based both on central and on local laboratory measurements, separately.

Box plots will be generated for the change in serum phosphorus levels from baseline for each treatment arm to the end of Stage 1 and to the end of Stage 2 on the FAS and PPS Populations.

In addition, plots will be provided with one curve for each treatment arm representing the mean change (±standard error of the mean (SEM)) from baseline in serum phosphorus levels at each time point to the end of Stage 1 and to the end of Stage 2 for the FAS and PPS Populations.

For the following secondary endpoints based on both central and local laboratory measurements, number and percentage calculated using the number of subjects with non-missing serum phosphorus level as denominators with corresponding exact 95%CIs will be provided by treatment group:

- Subjects with serum phosphorus level within the age related target range at each visit
- Subjects with serum phosphorus level within the age related normal range at each visit.

#### 4.8. Pharmacokinetic Evaluations

Not applicable.

# 4.9. Safety Analyses

Safety analyses will be conducted using the Safety Population.

## 4.9.1. Primary Safety Endpoint: Adverse Events

Adverse events will be coded using MedDRA and displayed in tables and listings using System Organ Class (SOC) and Preferred Term.

Analyses of adverse events will be performed for those events that are considered treatment emergent, where treatment emergent is defined as any adverse event with onset after the administration of study medication through the end of the study or any event that was present at baseline but worsened in intensity.

Adverse events are summarised by subject incidence rates, therefore, in any tabulation, a subject contributes only once to the count for a given adverse event (SOC or preferred term using the worst severity and the strongest relationship). The number of events will be reported as well in the summary tables. Multiple occurrences of the same TEAE in one subject during the same treatment in the trial will be counted as multiple events in the frequency counts for adverse events.

All TEAE summaries will be generated by treatment group and for both periods cumulatively, i.e. until end of stage 1 and until end of stage 2.

An overview of adverse events will be presented and will include the number and percentage of patients as well as the number of events with at least one:

- Treatment-emergent adverse events
- Treatment-related treatment-emergent adverse events
- Serious treatment-emergent adverse events
- Treatment-emergent adverse events leading to study drug discontinuation
- Treatment-emergent adverse events leading to Death
- Severe treatment-emergent adverse events

This table will be also repeated for any treatment-emergent adverse event of special interest (listed in Table 8 below). The overall summary of TEAEs will be also repeated by treatment group and overall maximum dose prescribed (see Table 9) during the trial. Results of the TEAE analysis by overall maximum dose prescribed may be confounded as the dose prescribed depends on the age. Therefore, a summary table with descriptive statistics for age will be provided for each overall maximum dose prescribed category by treatment.

The number and percentage of subjects as well as the number of events with the following adverse events will be presented by SOC and PT:

- with any treatment-emergent adverse event,
- with any treatment-emergent adverse events by causality assessed by the Investigator (related, unrelated),
- with any treatment-emergent adverse events by intensity assessed by investigator (mild, moderate, severe),
- with any treatment-emergent adverse events by age at randomisation (0-<2, 2-<6, 6-<12, 12-<=18). The denominator will be the number of patients in each age group category,
- with any treatment-emergent adverse event of special interest (listed in Table 8 below),
- with any serious treatment-emergent adverse event,
- with any serious treatment-related treatment-emergent adverse event,
- with any serious treatment-emergent adverse event that led to death,
- with any non-serious treatment-emergent adverse event,
- with any treatment-emergent adverse events that led to study drug discontinuation,
- and with any treatment-emergent adverse events started <4 weeks (<1 weeks, 1-<2 weeks and 2-<4 weeks will also be presented for more granularity), 4 to <12 weeks, 12 to <24 weeks, ≥24 weeks. The denominator is the number of patients at risk at the beginning of

the period (excluding those who have withdrawn or completed); i.e. in the category 2-<4 weeks, the denominator will include patients at risk/active at week 2.

Related events include Events with Certain or Probably/Likely or Possible as causality assessed by the investigator. Unrelated events include unlikely or unrelated as causality assessed by the investigator.

 Table 8
 Adverse Event of special interest definition

Events of special interest	MedDRA
Diarrhoea	MedDRA PT: -Diarrhoea
Potential of iron accumulation	MedDRA PT: -Cardiac iron overload -Haemochromatosis -Haemosiderosis -Hereditary haemochromatosis -Hepatic siderosis -Iron overload -Pulmonary haemosiderosis -Superficial siderosis of central nervous system
Masking of GI bleeding due to discoloured stool	MedDRA PT: -Faeces discoloured MedDRA SMQs: -SMQ GI haemorrhage
Events, which could be linked to (deficiencies in) growth and skeletal development and review of bone markers	SOC: Musculoskeletal and connective tissue disorder -HLT: Bone disorders NEC (from HLGT Bone disorders (excl congenital and fractures)) -HLT: Metabolic bone disorders NEC (from HLGT Bone disorders (excl congenital and fractures)) -HLGT: Fractures  SOC: Metabolism and nutrition disorders -HLT: Bone metabolism disorders (HLGT: Bone, calcium, magnesium and phosphorus metabolism disorders) -HLT: Calcium metabolism disorders (HLGT: Bone, calcium, magnesium and phosphorus metabolism disorders)

The maximum dose prescribed during the trial to be considered for each treatment is listed below:

Table 9 List of Maximum daily dose prescribed by treatment

PA21 (g PA21/day)	Phoslyra (mL/day)
≤2.5	<15
]2.5-5.0]	[15-25[

]5.0-7.5]	[25-35[
]7.5-10.0]	[35-44[
]10.0-12.5]	≥44
]12.5-15.0]	

Conversion between both units for PA21 (mg Iron and g PA21) will be obtained using the below table:

PA21 Dose (Units)		
mg iron	g PA21	Number of Tablets (using 1 tablet=2.5g PA21)
250	1.25	0.5
500	2.5	1
750	3.75	1.5
1000	5.0	2
1500	7.5	3
1750	8.75	3.5
2000	10.0	4
2250	11.25	4.5
2500	12.5	5
3000	15.0	6

In these tabulations, each subject will contribute only once (i.e., the most related occurrence or the most severe occurrence) to each of the incidence rates in the descriptive analysis, regardless of the number of episodes.

No formal hypothesis-testing analysis of adverse events incidence rates will be performed.

If a subject switches from a treatment to the other by mistake, then further summary tables will be generated to display for each treatment the adverse events reported under each received treatment.

All adverse events (treatment-emergent adverse events or non-treatment-emergent adverse events) occurring on study will be listed in subject data listings.

By-subject listings also will be provided for the following: subject deaths; serious adverse events; adverse events leading to study drug withdrawal; most common SOC based on PA21 total; adverse events of special interest.

If a subject switches from a treatment to the other by mistake, then further by-subject listings for adverse events will be provided, one by treatment.

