#### 2. STUDY DESIGN

# 2.1. Synopsis of Study Design

This study is a prospective, open-label, randomised, active-controlled, parallel group, multicenter, phase 3 study investigating the safety and efficacy of PA21 (Velphoro®) and calcium acetate (Phoslyra®) in paediatric and adolescent CKD subjects with hyperphosphataemia.

Approximately 130 subjects will be randomised to either PA21 (approximately 100 subjects) or to Phoslyra (approximately 30 subjects) with age as stratification factor.

Throughout the study, subjects randomised to receive PA21 will be provided with the most appropriate formulation i.e., either powder for oral suspension (for subjects <6 years) or chewable tablet (for subjects ≥6 years). For Phoslyra, only oral solution will be dispensed.

The study will consist of a maximum of 43 weeks including a screening period, a washout period, a treatment period split into 2 stages, and a follow-up period. Screening should be up to 4 weeks. The washout period should be of 1-3 weeks to allow sufficient time for washout of previous Phosphate Binders (PBs). Of note, subjects already receiving a PB but with age related serum phosphorus levels (Table H of the protocol) may be eligible for randomisation without a washout period. Treatment period will be split in 2 stages:

- Stage 1 is a dose titration period of PA21 and Phoslyra for up to 10 weeks. PA21 subjects will receive PA21 at a starting dose based on their age, as detailed in Table 3 from protocol. Phoslyra subjects will receive Phoslyra, either at a starting dose as detailed in Table 5 from protocol, or, if considered more appropriate by the Investigator, at an equivalent dose of their previous PB, calcium-based or sevelamer. Doses of PA21 or Phoslyra will be increased or decreased as required for efficacy (to achieve age specific target serum phosphorus level as indicated in Table 11 from protocol), provided a subject has been receiving that dose for a minimum of 2 weeks, and for safety or tolerability reasons at any time. Increases or decreases in dose and maximum doses are detailed in Table 4 from protocol for PA21, and Table 5 and Table 6 from protocol for Phoslyra. From Week 4, once a subject achieves the age specific target serum phosphorus level, as indicated in Table 11 from protocol, they can move to Stage 2.

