Table 14.2.6.3	Serum Phosphorus Level over Time according to the Age Related Normal Range - Central Laboratory Measurement (PPS Population)
Table 14.2.6.4	Serum Phosphorus Level over Time according to the Age Related Normal Range - Local Laboratory Measurement (PPS Population)
Table 14.3.1.1	Overview of Treatment-Emergent Adverse Events - Until End of Stage 1 (Safety Population)
Table 14.3.1.2	Overview of Treatment-Emergent Adverse Events - Until End of Stage 2 (Safety Population)
Table 14.3.1.3	Overview of Treatment-Emergent Adverse Events of Special Interest - Until End of Stage 1 (Safety Population)
Table 14.3.1.4	Overview of Treatment-Emergent Adverse Events of Special Interest - Until End of Stage 2 (Safety Population)
Table 14.3.1.5	Overview of Treatment-Emergent Adverse Events by Maximum Dose Prescribed (Safety Population)
Table 14.3.1.6	Treatment-Emergent Adverse Events by MedDRA System Organ Class and Preferred Term - Until End of Stage 1 (Safety Population)
Table 14.3.1.7	Treatment-Emergent Adverse Events by MedDRA System Organ Class and Preferred Term - Until End of Stage 2 (Safety Population)
Table 14.3.1.8	Serious Treatment-Emergent Adverse Events by MedDRA System Organ Class and Preferred Term - Until End of Stage 1 (Safety Population)
Table 14.3.1.9	Serious Treatment-Emergent Adverse Events by MedDRA System Organ Class and Preferred Term - Until End of Stage 2 (Safety Population)

Table 14.3.1.10	Non-serious Treatment-Emergent Adverse Events by MedDRA System Organ Class and Preferred Term - Until End of Stage 1 (Safety Population)
Table 14.3.1.11	Non-serious Treatment-Emergent Adverse Events by MedDRA System Organ Class and Preferred Term - Until End of Stage 2 (Safety Population)
Table 14.3.1.12	Treatment-Emergent Adverse Events Related to Study Drug by MedDRA System Organ Class and Preferred Term - Until End of Stage 1 (Safety Population)
Table 14.3.1.13	Treatment-Emergent Adverse Events Related to Study Drug by MedDRA System Organ Class and Preferred Term - Until End of Stage 2 (Safety Population)
Table 14.3.1.14	Serious Treatment-Emergent Adverse Events Related to Study Drug by MedDRA System Organ Class and Preferred Term - Until End of Stage 1 (Safety Population)
Table 14.3.1.15	Serious Treatment-Emergent Adverse Events Related to Study Drug by MedDRA System Organ Class and Preferred Term - Until End of Stage 2 (Safety Population)

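### The adverse event table by maximum prescribed dose (SAP Table 14.3.1.5) can show a dose gradient where none exists, and the age caveat does not cover this

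*SAP*

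**What the plan says.** Section 4.9.1 of the SAP states: "The overall summary of TEAEs will be also repeated by treatment group and overall maximum dose prescribed (see Table 9) during the trial". Table 9 supplies six PA21 categories and five Phoslyra categories, and each subject falls into one of them. The overview being repeated includes a row for TEAEs leading to discontinuation of study drug. In the list of outputs (section 7.1), Table 14.3.1.5 is the only adverse event table organised by dose.

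The limitation acknowledged is "Results of the TEAE analysis by overall maximum dose prescribed may be confounded as the dose prescribed depends on the age", and the response is "Therefore, a summary table with descriptive statistics for age will be provided for each overall maximum dose prescribed category by treatment".

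Section 2.1 describes how dose moves. "Stage 1 is a dose titration period of PA21 and Phoslyra for up to 10 weeks". Doses go up or down for efficacy "provided a subject has been receiving that dose for a minimum of 2 weeks, and for safety or tolerability reasons at any time". Titration may continue during the 24 weeks of Stage 2. PA21 starting doses depend on age. Phoslyra may start at an equivalent of the previous binder.

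**The concern.** Maximum prescribed dose is not a baseline characteristic. It is settled only when follow-up ends, and it depends on two things that are tied to adverse events: staying in the study and tolerating the drug. Two consequences follow.

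- A subject who stops early because of an event has no chance of reaching a higher category. The discontinuation row of the table is therefore linked to the grouping variable by construction.
- All of a subject's events are credited to the maximum, including those that began before the dose was raised to that level and those that began after it was lowered.

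Neither consequence has anything to do with age, so a table of age by dose category cannot reveal or correct them. What is at stake is the reading of the only planned table that links adverse events to dose, in a study whose introduction (section 1.1) gives information on safety and dosing as an aim.

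**Working it through.** **No SAP figure is in dispute.** The point concerns how the table is built, so there is no stated number to reproduce.

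**Passages side by side.** Section 4.9.1 fixes one dose category per subject over the whole trial, while section 2.1 lets dose change for up to 10 weeks in Stage 1 and then for 24 weeks in Stage 2 (10 + 24 = 34 weeks). No TEAE table by dose at onset or by time at dose is listed in section 7.1. Denominators of subjects still at risk are specified for the time-of-onset tables, but those are not split by dose. The exposure tables (section 4.6) are repeated by age, gender, region and formulation, but not by maximum-dose category.

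**Illustration with no true dose effect.** Every input below is an assumption, except that the 34-week length and the two-week minimum between efficacy changes follow section 2.1. Each scenario has 200,000 subjects. All start at one level, with a possible one-level increase at weeks 2, 4, 6 and 8 and no reductions. Withdrawal for other reasons is 0.4% per week.

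| Scenario | Weekly event risk | Events causing withdrawal | Chance of each increase | Overall withdrawal |
|---|---|---|---|---|
| A | 5% throughout | 15% | 40% | 33% |
| B | 5%, then 2.5% from week 4 | 15% | 40% | 24% |
| C | 10%, then 4% from week 4 | 10% | 40% | 26% |
| D | 5% throughout | 15% | 60% | 32% |

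For comparison, section 4.1 allows for about 30% drop-out. Results, never-escalated group against highest maximum-dose group:

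| Scenario | Discontinued for an event | Any event | Mean weeks on treatment | Events credited to an escalated group that began below its maximum |
|---|---|---|---|---|
| A | 31.2% v 17.0% | 76.4% v 79.5% | 22.5 v 30.5 | 15-23% |
| B | 22.7% v 9.1% | 60.8% v 58.6% | 24.1 v 31.7 | 21-29% |
| C | 27.8% v 9.1% | 76.9% v 77.4% | 22.6 v 31.6 | 26-35% |
| D | 45.7% v 17.0% | 73.6% v 79.3% | 13.7 v 30.7 | 15-23% |

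The discontinuation row shows a clear gradient although dose has no effect. The any-event row hardly moves: the largest difference is 79.3 - 73.6 = 5.7 points, in D.

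**Varying the starting dose.** With 3% weekly risk, one quarter of events causing withdrawal, a 50% chance of each increase, no reductions and starting levels spread evenly over four of six categories, the lowest category shows 44% discontinuing for an event but holds only 2% of subjects. The other categories run from 29% down to 19%. The gradient survives, but its extreme sits in a very small group.

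**Assigning events to the dose in force at onset.** Events divided by weeks at that dose, lowest against highest level:

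- Constant risk (A and D): about 0.050 per week at every level, so the false gradient disappears.
- Falling risk (B): 0.036 v 0.025 per week.
- Falling risk (C): 0.067 v 0.040 per week.

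When risk falls with time, part of the gradient remains because low doses are also early doses. A table by dose at onset therefore needs a split by time on treatment.

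**Numbers per cell.** About 100 PA21 subjects over six categories average 100/6 = 16.7 each. With the reduced minimum of 60 in section 5, the average is 60/6 = 10. Scenario A's 31.2% v 17.0% then amounts to 5.2 v 2.8 subjects at 16.7 per category, or 3.1 v 1.7 at 10.

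**The case against.** The other side has several sound points.

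- **Reach.** Table 14.3.1.5 is one supplementary repeat of an overview. Section 4.9.1 rules out formal testing of adverse event rates, and the primary safety endpoint is reported by arm in tables that do not use this variable. This stands, and it is why the point is minor.
- **A caveat already exists.** The SAP does warn against a causal reading. But the warning names only age, and so does its remedy.
- **Other outputs help.** Time-of-onset tables use at-risk denominators, events leading to withdrawal are tabulated and listed, and dosing is listed. These soften the gap without closing it, because no table among them relates adverse events to the dose in force.
- **Noise.** With 10 to 17 subjects per category, chance may outweigh the bias. That is a reason for caution in reading the table, not a reason to leave the caveat incomplete.
- **Current dose is not a clean substitute.** It is confounded with time on treatment, as scenarios B and C show. It also ignores lagged effects such as iron accumulation (Table 8), for which maximum dose is a defensible summary. This stands, and it argues for adding a table rather than replacing one.

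A reader might go further and infer that the table will make higher doses look safer, or that early withdrawals collect in the lowest dose category. The SAP supports neither. Events after a dose reduction stay credited to the earlier maximum, which pushes the other way, and the simulation left reductions out. Starting doses vary with age or previous binder, so an early withdrawal is held near its own starting category, which need not be the lowest.

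**Conclusion.** The point holds as a limited one. Grouping by maximum prescribed dose conditions on later retention and tolerability, so the by-dose comparison in Table 14.3.1.5 can show a gradient with no true dose effect. The row for events leading to discontinuation is the most exposed; the any-event row is little affected. The stated age caveat and age table do not address this.

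The size and net direction cannot be derived from the SAP. The contrast of 23-46% against 9-17% in discontinuations, and the 15-35% of events credited to a maximum not yet reached, illustrate the mechanism under assumed event rates, withdrawal and step-up probabilities, without dose reductions. They do not predict this trial. Nor does the point show that the planned safety conclusions are wrong: the table is descriptive, and the primary endpoint and by-arm adverse event tables are unaffected. The grade is minor, with a cheap improvement available.

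**What to change.** Keep Table 14.3.1.5 and make three changes. All concern analysis and reporting only; none bears on any dosing rule.

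1. **Widen the caveat in section 4.9.1**, and footnote the table: maximum dose depends on time in study and on tolerability as well as age, and the counts include events that began at other doses.
2. **Show exposure duration per maximum-dose category**, for example as extra rows in the planned table of age by category.
3. **Add one supplementary table** of TEAEs by the Table 9 category in force at onset, with patient-weeks at that dose as denominator, split by treatment period. The existing onset bands (under 4, 4 to under 12, 12 to under 24, and 24 weeks or more) would serve.

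The data are already in use: section 4.6 works from start date, end date and prescribed daily dose for each administration, and section 4.2.8.5 handles event onset dates.

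The costs are one more derivation and table, sparse cells once dose and period are crossed, and no capture of lagged effects. A tie rule is also needed for partial onset dates near a dose change, because the section 4.2.8.5 imputation generally moves such dates to the first administration or to the start of the month or year, and so towards the earlier dose.

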Table 14.3.1.16	Serious Treatment-Emergent Adverse Events that Led to Death by MedDRA System Organ Class and Preferred Term - Until End of Stage 1 (Safety Population)
Table 14.3.1.17	Serious Treatment-Emergent Adverse Events that Led to Death by MedDRA System Organ Class and Preferred Term - Until End of Stage 2 (Safety Population)
Table 14.3.1.18	Treatment-Emergent Adverse Events that Led to Study Drug Withdrawal by MedDRA System Organ Class and Preferred Term - Until End of Stage 1 (Safety Population)
Table 14.3.1.19	Treatment-Emergent Adverse Events that Led to Study Drug Withdrawal by MedDRA System Organ Class and Preferred Term - Until End of Stage 2 (Safety Population)
Table 14.3.1.20	Treatment-Emergent Adverse Events of Special Interest by MedDRA System Organ Class and Preferred Term - Until End of Stage 1 (Safety Population)
Table 14.3.1.21	Treatment-Emergent Adverse Events of Special Interest by MedDRA System Organ Class and Preferred Term - Until End of Stage 2 (Safety Population)

Table 14.3.1.22	Treatment-Emergent Adverse Events by Maximum Intensity by MedDRA System Organ Class and Preferred Term - Until End of Stage 1 (Safety Population)
Table 14.3.1.23	Treatment-Emergent Adverse Events by Maximum Intensity by MedDRA System Organ Class and Preferred Term - Until End of Stage 2 (Safety Population)
Table 14.3.1.24	Treatment-Emergent Adverse Events by Causality by MedDRA System Organ Class and Preferred Term - Until End of Stage 1 (Safety Population)
Table 14.3.1.25	Treatment-Emergent Adverse Events by Causality by MedDRA System Organ Class and Preferred Term - Until End of Stage 2 (Safety Population)
Table 14.3.1.26	Treatment-Emergent Adverse Events by Time of Onset by MedDRA System Organ Class and Preferred Term - Until End of Stage 1 (Safety Population)
Table 14.3.1.27	Treatment-Emergent Adverse Events by Time of Onset by MedDRA System Organ Class and Preferred Term - Until End of Stage 2 (Safety Population)
Table 14.3.1.28	Overview of Treatment-Emergent Adverse Events by Age - Until End of Stage 1 (Safety Population)
Table 14.3.1.29	Overview of Treatment-Emergent Adverse Events by Age - Until End of Stage 2 (Safety Population)
Table 14.3.1.30	Treatment-Emergent Adverse Events by Age by MedDRA System Organ Class and Preferred Term - Until End of Stage 1 (Safety Population)
Table 14.3.1.31	Treatment-Emergent Adverse Events by Age by MedDRA System Organ Class and Preferred Term - Until End of Stage 2 (Safety Population)

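### The table of adverse events by time of onset gives percentages over periods of unequal length without patient-time, so its rows cannot be read as a time trend

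*SAP*

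**What the plan says.** Section 4.9.1 lists the content of the tables by system organ class (SOC) and preferred term (PT): "The number and percentage of subjects as well as the number of events with the following adverse events will be presented by SOC and PT". One item is the breakdown by time of onset, "with any treatment-emergent adverse events started <4 weeks (<1 weeks, 1-<2 weeks and 2-<4 weeks will also be presented for more granularity", followed by "4 to <12 weeks, 12 to <24 weeks, ≥24 weeks. The denominator is the number of patients at risk at the beginning of" the period. The example given is that "in the category 2-<4 weeks, the denominator will include patients at risk/active at week 2".

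Section 7.1 plans two such tables: 14.3.1.26, up to the end of Stage 1, and 14.3.1.27, "Treatment-Emergent Adverse Events by Time of Onset by MedDRA System Organ Class and Preferred Term - Until End of Stage 2 (Safety Population".

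On counting, Section 4.9.1 says that "in any tabulation, a subject contributes only once to the count for a given adverse event", and it repeats the rule in similar terms after the dose conversion table. It does not say whether this means once per onset period or once per table. Numbers of events are also shown, and repeat occurrences count as separate events.

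The collection window is "any adverse event with onset after the administration of study medication through the end of the study". Section 2.1 sets the stages: "Stage 1 is a dose titration period of PA21 and Phoslyra for up to 10 weeks", with a possible move from Week 4, then 24 weeks of Stage 2 and a follow-up 14 days after the last visit.

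No adverse event table in Section 4.9.1 or 7.1 carries patient-time or a rate per unit of follow-up. Duration of exposure is summarised separately in Section 4.6, by stage and overall, but not by onset period.

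**The concern.** The only purpose of this table is to show when events start. A reader will compare rows, for example to see whether diarrhoea, an event of special interest in Table 8 of the SAP, is early or persistent. The chosen denominator removes children who left before a period began. It does not account for how long the remaining children were observed within the period. A 12-week row therefore collects more children with an event than a 4-week row at the same underlying rate.

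The last row adds a second problem, because its length depends on how quickly a child entered Stage 2. If the two arms move at different speeds, that row compares unequal follow-up between arms.

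Section 4.9.1 warns of confounding by age in the table by maximum dose and adds a supporting table for it. The onset table has no comparable caution.

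**Working it through.** **Inputs from the SAP.** Onset periods: Section 4.9.1. Stage and follow-up lengths: Section 2.1. Dropout of 30%: Section 4.1, used in one sensitivity row only. The SAP gives no event rate, so the weekly rates below are assumptions, shown over a range.

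**Check on the timeline.** Screening 4 + washout 3 + Stage 1 10 + Stage 2 24 + follow-up 2 = 43 weeks, which matches the maximum duration in Section 2.1.

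**Period lengths.** The main rows last 4 weeks (1 + 1 + 2), 12 − 4 = 8 weeks and 24 − 12 = 12 weeks. The last row for completers lasts between 4 + 24 + 2 − 24 = 6 weeks (move at Week 4) and 10 + 24 + 2 − 24 = 12 weeks (move at Week 10).

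**Formulas**, for weekly rate h and a period from week a to week b of length L = b − a:
- Counted once per period: 1 − exp(−hL).
- Counted once per table (first onset only, same denominator): exp(−ha) − exp(−hb).
- Once per period with dropout at rate d: [h/(h + d)] × [1 − exp(−(h + d)L)]. Here 30% is spread evenly in hazard over 34 weeks, so d = −ln(0.7)/34 = 0.0105.

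Worked case, h = 0.02, once per period: 1 − exp(−0.08) = 7.7%; 1 − exp(−0.16) = 14.8%; 1 − exp(−0.24) = 21.3%; last row from 1 − exp(−0.12) = 11.3% to 21.3%.

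**Percentages the four main rows would show**

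| Assumed weekly rate and counting | <4 | 4 to <12 | 12 to <24 | ≥24 |
|---|---|---|---|---|
| Constant 0.5%, per period | 2.0 | 3.9 | 5.8 | 3.0–5.8 |
| Constant 2%, per period | 7.7 | 14.8 | 21.3 | 11.3–21.3 |
| Constant 2%, per period, 30% dropout | 7.5 | 14.2 | 20.1 | 11.0–20.1 |
| Constant 2%, once per table | 7.7 | 13.6 | 16.8 | 7.0–13.2 |
| Constant 5%, per period | 18.1 | 33.0 | 45.1 | 25.9–45.1 |
| Constant 5%, once per table | 18.1 | 27.0 | 24.8 | 7.8–13.6 |
| 2%, halving at Weeks 4, 12 and 24, per period | 7.7 | 7.7 | 5.8 | 1.5–3.0 |
| 5% in Weeks 0–2, 3% in Weeks 2–4, then 1%, per period | 14.8 | 7.7 | 11.3 | 5.8–11.3 |

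At a constant 2%, the third main row is 21.3/7.7 = 2.8 times the first. Against the 1-week split (2.0%) the ratio is more than tenfold. In the halving case, a rate that falls by half at Week 4 appears as no change. In the last case the early concentration is visible, but 7.7% and then 11.3% are shown for two periods with the same 1% rate.

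**Stage 1 table.** A child who enters Stage 2 at Week 4, 6, 8 or 10 spends 0, 2, 4 or 6 weeks in the 4 to <12 week row. At 2% per week those children would show 0%, 3.9%, 7.7% and 11.3%.

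**With patient-time.** Take 100 children without dropout and 0.02 events per child-week. The first three main rows have 8 events in 400 patient-weeks, 16 in 800 and 24 in 1,200. The last has 12 in 600 to 24 in 1,200. Every row gives 2.0 per 100 patient-weeks.

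**The case against.** Several points on the other side are sound.

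- **The <4-week row is a main category.** The 1-, 1- and 2-week splits are additional detail. A reader might infer that the table would show events rising throughout treatment even when the true rate drops sharply after the first weeks. The SAP does not support that. A strong early concentration makes the <4-week row the highest (14.8% in the last line of the table above), and the ≥24-week row is level with or below the one before it.
- **The counting rule may limit the effect.** If a subject counts once per table, children who already had the event stay in later denominators. At 5% per week the profile then peaks at 4 to <12 weeks and falls. The SAP does not settle which rule applies.
- **Readers have partial remedies.** Row labels show the period lengths (except the open one), event counts are given, all events are listed, and no adverse event testing is planned. This allows a rough correction. It does not supply the patient-weeks in each period, least of all for the open last row and the truncated Stage 1 row.
- **Rates will be sparse.** With about 30 Phoslyra subjects planned, rates for each SOC and PT would be unstable. This is a reason to limit the rates to a few rows. The patient-weeks themselves are one figure per period and arm.

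A reader might also infer that sparser visits later in the study add to the apparent rise. They do not: the periods are defined by onset, and events missed between visits would lower the later rows.

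**Conclusion.** The concern holds in a limited form. The onset percentages in Tables 14.3.1.26 and 14.3.1.27 are not comparable across rows as a time trend, because the periods differ in length and the denominator is a head count. For uncommon events at a constant rate, period length alone makes the 12 to <24 week row nearly three times the <4-week row. The ratio is little changed by 30% dropout, and at 2% per week it is still 16.8/7.7 = 2.2 if subjects are counted once per table.

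It does not follow that the table would always show a rise, or would hide a steep early effect. The size rests on assumed weekly rates, on nominal visit timing and, for the per-period figures, on one of two possible counting rules. The table is descriptive and no efficacy conclusion depends on it. This is a worthwhile improvement to a safety display, not a flaw in the trial's main analysis.

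**What to change.** In Tables 14.3.1.26 and 14.3.1.27:

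1. For each onset period and arm, give the patient-weeks actually spent in the period, truncated at withdrawal, completion or, in the Stage 1 table, the end of Stage 1.
2. Give events per 100 patient-weeks, at least for overall treatment-emergent events and for the events of special interest such as diarrhoea.
3. State whether a subject is counted once per onset period or once per table.
4. Footnote the unequal period lengths, and base any statement about time trend on the rates.

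The cost is a little extra programming from dates already collected. The downside is imprecise rates in small cells, especially for Phoslyra, so the rates need not be extended to every SOC and PT row.
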